6.12.5 Physical Examinations

Physical examination dates will be listed by subject. Clinically significant findings are recorded as adverse events.

6.12.6 ECOG Performance Status

ECOG performance status mean and mean change from baseline during the randomized treatment period will be tabulated by treatment arm.

All ECOG performance status data will be listed by subject.

6.13 Pharmacokinetics Analysis

Pharmacokinetic (PK) analysis will be conducted using population-based methods. Details of the Pharmacokinetic analysis will be provided in a separate PK analysis plan.

The KW-0761 concentrations at each scheduled time point of collection will be tabulated for subjects in the KW-0761 arm and for subjects who are randomized to vorinostat and crossed over into the KW-0761 arm. If serum KW-0761 concentration is below the lower limit of quantification (BLQ, <1.25 ng/mL), the concentration will be shown as 'BLQ' in the data listing, and the data will be considered to be 0 ng/mL when calculating descriptive statistics.

If the mean, minimum, median, or maximum is calculated to be below the lower limit of quantification, it will be shown as 'BLQ' in the summary table. If the mean is below the lower limit of quantification, standard deviation will be shown as '-' in the summary table.

All KW-0761 concentration data will be listed by subject.

6.14 Analysis of Immunogenicity Data

[figure not shown]
Samples to detect anti-KW-0761 antibodies for the analysis of immunogenicity will be taken at baseline (Cycle 1, Day 1), Day 26-28 of Cycle 1, every 8 weeks thereafter, and at the end of treatment.

Anti-KW-0761 antibody status (positive, negative, and inconclusive) will be tabulated at each scheduled time point and overall at post-baseline for subjects in the KW-0761 arm and separately for those subjects who are randomized to vorinostat but crossed over into the KW-0761 arm. Anti KW-0761 antibody status will be determined using anti-KW-0761 antibody assay result and KW-0761 concentration value as outlined below:

- Positive: When the sample is positive in both screening assay and confirmatory assay, the sample status is considered to be Positive.
- Negative: When the sample is negative in screening assay and KW-0761 concentration at the same time point is equal to or less than drug tolerance limit (16000 ng/mL), or when the sample is positive in screening assay and negative in confirmatory assay, the sample status is considered to be Negative.
- Inconclusive: When the sample is negative in screening assay and KW-0761 concentration at the same time point is above the drug tolerance limit (>16000 ng/mL), the sample status is considered to be Inconclusive. When the sample is negative in screening assay and KW-0761 concentration is not measured, the sample status is considered to be inconclusive.

Anti KW-0761 Antibody Status

-decision tree-

The number and percentage of subjects with a positive neutralizing antibody test result will also be presented for each scheduled time point and overall at post-baseline. For each subject, overall is defined as positive if at least one post-baseline neutralization test result is positive.

Additionally, a summary of subjects with a positive overall assay at any time post-baseline and who experienced infusion reaction will be presented.

All immunogenicity data will be listed by subject.

6.15 Analysis of CCR4 and Other Biomarkers

CCR4 expression results will be listed by subject.

A separate analysis plan will be prepared to detail the CCR4 and other biomarker analyses.

6.16 Other Data Considerations

All other information recorded in the Case Report Form (CRF) (e.g., inclusion and exclusion criteria, natural ligands assessment, genetic determinants (i.e., Fc-gamma receptor polymorphisms), results of serum pregnancy test, etc.) will be listed by subject.

8 PROGRAMMING CONSIDERATIONS

All tables, data listings, figures (TLFs), and statistical analyses will be generated using SAS[®] Version 9.3 or higher. Computer-generated table output will adhere to the following specifications.

8.1 Table, Listing, and Figure Format

8.1.1 General

- 1) All TLFs will be produced in landscape format.
- 2) All TLFs will be produced using the Courier New font, size 8.
- 3) The data displays for all TLFs will have a 1.5-inch binding margin on top of a landscape oriented page and a minimum 1-inch margin on the other 3 sides.
- 4) Headers and footers for figures will be in Courier New font, size 8.
- 5) Legends will be used for all figures with more than 1 variable, group, or item displayed.
- 6) TLFs will be in black and white (no color).
- 7) Specialized text styles, such as bolding, italics, borders, shading, and superscripted and subscripted text, will not be used in the TLFs. On some occasions, superscripts 1, 2, or 3 may be used (see below).
- 8) Only standard keyboard characters will be used in the TLFs. Special characters, such as non-printable control characters, printer-specific, or font-specific characters, will not be used. Hexadecimal-derived characters will be used, where possible, if they are appropriate to help display math symbols (e.g., μ). Certain superscripts (e.g., cm^2) will be employed on a case-by-case basis.
- 9) Mixed case will be used for all titles, footnotes, column headers, and programmer-supplied formats.

8.1.2 Headers

- 1) All output should have the following header at the top of the page:

Kyowa Kirin Pharmaceutical Development, Inc.
Study: Protocol 0761-010

Date: DD-MMM-YYYY
Page n of N

All output should have a date (date output was generated) and page number. TLFs should be internally paginated in relation to the total length (i.e., the page number should appear sequentially as page n of N, where N is the total number of pages in the table).

8.1.3 Display Titles

- 1) Each TLF should be identified by a numeral, and the designation (i.e., Table 1) should be centered above the title. A decimal system (x.y and x.y.z) should be used to identify TLFs with related contents. The title is centered in initial capital characters. The analysis set should be identified on the line immediately following the title. The title and table designation are single spaced. A solid line spanning the margins will separate the display titles from the column headers. There will be 1 blank line between the last title and the solid line.

Table x.y.z
First Line of Title
Second Line of Title if Needed
Safety Analysis Set

8.1.4 Column Headers

- 1) Column headings should be displayed immediately below the solid line described above in initial upper-case characters. The variable (or characteristic) column will be on the far left followed by the treatment group columns, total column (if applicable), and p-value column (if applicable).
- 2) For numeric variables, include “unit” in column or row heading when appropriate.
- 3) Analysis set sizes will be presented for each treatment group in the column heading as (N=xx) (or in the row headings if applicable). This is distinct from the ‘n’ used for the descriptive statistics representing the number of subjects in the analysis set.
- 4) The order of treatments in the mock-up tables and listings will be: Vorinostat and KW-0761, and Total (if applicable).

8.1.5 Body of the Data Display

- 1) Listings will be sorted for presentation in order of treatment groups as above, subject number, collection day, and collection time.
- 2) If the categories of a parameter are ordered, then all categories between the maximum and minimum category should be presented in the table, even if n=0 for all treatment groups in a given category that is between the minimum and maximum level for that parameter. For example, the frequency distribution for symptom severity would appear as:

Severity Rating	n
severe	0
moderate	8
mild	3

Where percentages are presented in these tables, any counts of 0 will be presented as 0 and not as 0 (0%).

- 3) If the categories are not ordered (e.g., Medical History, Reasons for Discontinuation from the Study, etc.), then only those categories for which there is at least 1 subject represented in 1 or more groups should be included.
- 4) An Unknown or Missing category should be added to any parameter for which information is not available for 1 or more subjects.
- 5) Unless otherwise specified, the estimated mean and median for a set of values should be printed out to 1 more significant digit than the original values, and standard deviations should be printed out to 2 more significant digits than the original values. The minimum and maximum should report the same significant digits as the original values. For example, for systolic blood pressure:

N	XX
Mean	XXX.X
Std Dev	X.XX
Median	XXX.X
Minimum	XXX
Maximum	XXX

- 6) Data in columns of a table should be formatted as follows:
 - alphanumeric values are left-justified;
 - whole numbers (e.g., counts) are right-justified; and
 - numbers containing fractional portions are decimal aligned.
- 8) Percentage values should be printed with 1 digit to the right of the decimal point in parentheses 1 space after the count (e.g., 7 (12.8), 13 (5.4)). Less-than-signs “<0.1” should be printed when values are >0.0 and <0.1 (not 0.0). Unless otherwise noted, for all percentages, the number of subjects in the analysis set for the treatment group who have an observation will be the denominator.
- 9) Tabular display of data for concomitant medications and all tabular displays of adverse event data should be presented by the body system, drug class, or SOC with the highest occurrence in the total column in decreasing order. Within the body system, drug class and SOC, drugs (by ATC1 code) and adverse events (by preferred term) should be displayed in decreasing order. If incidence for more than 1 term is identical, they should then be sorted alphabetically.
- 10) Missing data should be represented on subject listings as either a hyphen (“-”) with a corresponding footnote (“ - = unknown or not evaluated”), or as “N/A”, with the footnote “N/A = not applicable”, whichever is appropriate. Missing descriptive statistics due to non-estimability should be reported as “-”.
- 11) Date should be printed in SAS[®] YYMMDD10.format (“YYYY-MM-DD”: 2000-07-01). Missing portions of dates will not be presented on subject listings (2000-07). Dates that are missing because they are not applicable for the subject are output as “N/A”, unless otherwise specified.

- 12) All observed time values must be presented using a 24-hour clock HH:MM:SS format (e.g., 01:35:45, or 11:26). Time will only be reported if it was measured as part of the study.

8.1.6 Footnotes

- 1) A solid line spanning the margins will separate the body of the data display from the footnotes.
- 2) All footnotes will be left justified with single-line spacing immediately below the solid line underneath the data display.
- 3) Footnotes should always begin with “Note:” if an informational footnote, or asterisks and other non-numeric symbols if an annotated footnote. Each new footnote starts on a new line.
- 4) Footnotes will be present on the page where they are first referenced and thereafter on each page of the table, unless the footnote is specific only to certain pages. Subject specific footnotes should be avoided.
- 5) Footnotes will be used sparingly and must add value to the table, figure, or data listing. If more than 4 footnotes are planned, then a cover page may be used to display footnotes, and only those essential to comprehension of the data will be repeated on each page. Footnotes should not repeat definitions already provided in the SAP.
- 6) The last line of the footnote section will be a standard source line that indicates the data source called in by the program, the name of the program used to produce the data display, and the listing source (i.e., ‘Data source: xyzabc.sas7bdat Program source: myprogram.sas Listing source: 16.x.y.z’).

8.2 Data-Handling Rules

This section describes naming conventions and rules for calculations that would be common to all applicable tables. Some rules specific to a table can be found in the relevant mock-ups.

8.2.1 Visits

- 1) Relative Study Day: The first day of treatment is Day 1. A minus (-) sign indicates days prior to the start of treatment (e.g., Day -5 represents 5 days before start of therapy. There is no Day 0.). The relative study day for a specific visit is calculated as (Visit Date - Date of First Dose +1).
- 2) Baseline: For all study variables, baseline is defined as the last measurement obtained prior to the first dose of the study medication.

8.2.2 Demographics and Baseline Characteristics

- 1) Age = (Screening visit date - date of birth + 1) / 365.25 and truncated to complete years.

- 2) $BSA (m^2) = ([Height(cm) \times Weight(kg)] / 3600)^{1/2}$
- 3) $BMI (kg/m^2) = Weight(kg) / [Height(m)]^2$

8.2.3 Prior and Concomitant Medications

- 1) Prior and concomitant medications will be coded and classified using the WHO Drug Dictionary (September 2012). The specific dictionary version will be provided in the actual tables/listings.
- 2) Counting rules for prior and concomitant medications: Prior medications include medications that were taken within 30 days prior to study entry and stopped prior to start of randomized treatment. Concomitant medications during randomized treatment period include medications that started at any time and were taken at any time after the start of randomized treatment until the end of the entire randomized treatment period. Concomitant medications during the crossover portion include medications that started at any time and were taken at any time after the start of KW-0761 during the crossover portion until the end of the entire treatment period.
- 3) Medications missing both start and stop dates, or having a start date prior to the last dose of study drug and missing the stop date, or having a stop date after the start of study drug and missing the start date, will be counted as concomitant. When partial dates are present in the data, both a partial start date and/or a partial stop date will be evaluated to determine whether it can be conclusively established that the medication either ended prior to the start of study drug or started after the end of study drug. If the above cannot be conclusively established based on the partial and/or present dates, then the medication will be counted as concomitant.

8.2.4 Safety

- 1) If multiple results (e.g., lab test results) are reported at a study visit, then the most deviant lab result reported for that visit will be used in that visit summary.
- 2) Adverse events will be coded and classified using the MedDRA dictionary. The specific dictionary version will be provided in the actual tables/listings.
- 3) Counting rules for adverse events: Adverse events with missing start dates, but with stop dates either overlapping into the treatment period or missing, will be counted as treatment-emergent, taking the worst-case approach. Special care will be taken regarding partial dates with similar logic to that of the prior/concomitant medications applied.
- 4) For purposes of flagging individual subject data listings, laboratory abnormalities are defined as values above or below the normal range.

8.2.5 SAS[®] Procedures

This section provides sample SAS[®] code to illustrate statistical tests specified in the statistical methods section. All computer output from SAS[®] statistical procedures serving as a basis for extracted results (e.g., LIFETEST) will be retained for quality control procedures and will be included in CSR appendices.

- 1) Stratified Log Rank test for PFS between treatment:

```
proc lifetest method=KM;
    time PFS*censor(1);
    strata type stage region/group=trt;
run;
```
- 2) Hazard ratio from Cox proportional hazard model for PFS:

```
proc phreg;
    model PFS*censor(1)=trt type stage region/risklimits ties=efron;
run;
```
- 3) CMH test for ORR between treatment:

```
proc freq;
    tables type*stage*region*trt*resp/cmh;
run;
```
- 4) Exact 95% confidence interval on ORR and exact 95% unconditional confidence interval for the risk difference:

```
proc freq;
    tables trt*resp;
    exact riskdiff;
run;
```
- 5) ANCOVA for change in QoL score between treatment:

```
proc mixed;
    class trt type stage region timept usubjid;
    model QoL_chng = trt type stage region base_QoL timept
        trt*timept/solution;
    repeated timept / subject=usubjid type=un;
    lsmeans trt/pdiff cl;
run;
```
- 6) Wilcoxon Rank Sum test for change in Likert Scale score between treatment:

```
proc npar1way wilcoxon hl;
    class trt;
    var QoL_chng;
run;
```

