6.11.2 Efficacy Analysis Methodology

6.11.2.1 Analysis of Primary Efficacy Variable

The primary comparison of progression-free survival between KW-0761 and vorinostat will be performed on the ITT set based upon the results of the on-site Investigator's assessment using a stratified Log-rank test at the one-sided 2.5% significance level. Stratification is done by disease type (MF or SS), disease stage (IB/II or III/ IV), and region (U.S., Japan, and Rest of World). A Cox proportional hazard model with treatment, disease type, disease stage, and region (U.S., Japan, and Rest of World) as covariates will be used to assess the magnitude of the treatment difference in PFS. The hazard ratio along with the 95% confidence interval obtained from the Cox proportional hazard model will be presented. Additional analyses may be performed adjusting for treatment and other baseline characteristics.

The median PFS and the 2-sided 95% confidence interval for each treatment will be estimated using the Kaplan-Meier survival analysis methods. Kaplan-Meier estimate of PFS rates and the corresponding 95% confidence interval will also be provided for each treatment arm by 6 months intervals. Plots of the Kaplan-Meier estimate of the survival distribution function over time for PFS will be presented by treatment arm.

The primary analysis of PFS will be performed when 255 total PFS events have been observed or 24 months after the last randomized subject's first dose, whichever comes first.

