Rate (%) of Being Alive without Progression for at Least***		
6 months (95% CI)	xx.x (xx.x, xx.x)	xx.x (xx.x, xx.x)
12 months (95% CI)	xx.x (xx.x, xx.x)	xx.x (xx.x, xx.x)
18 months (95% CI)	xx.x (xx.x, xx.x)	xx.x (xx.x, xx.x)
24 months (95% CI)	xx.x (xx.x, xx.x)	xx.x (xx.x, xx.x)
Etc.		

Note: Percentage is calculated using the number of subjects in the column heading as the denominator.

* 95% CIs are obtained from SAS proc lifetest using loglog transformation.

** Hazard ratio and 95% CI are based on Cox proportional hazards model with treatment, disease type, disease stage, and region as covariates. P-value (two-sided) is obtained from a stratified log rank test (one-sided test at 0.025 level or equivalently two-sided test at 0.05 level) with disease type, disease stage, and region as stratification factors.

*** Kaplan-Meier estimate.

The following tables will have similar layout as Table 14.2.1.1:

Table 14.2.1.2
Summary of Progression-Free Survival (PFS) Based on Investigator's Assessment
Sensitivity Analysis 1
Intent-to-Treat Set

Table 14.2.1.3
Summary of Progression-Free Survival (PFS) Based on Investigator's Assessment
Sensitivity Analysis 2
Intent-to-Treat Set

Table 14.2.1.4
Summary of Progression-Free Survival (PFS) Based on Investigator's Assessment - Worst Case Sensitivity Analysis
Sensitivity Analysis 3
Intent-to-Treat Set

<<Programming Note: Add the corresponding PFS definition in the footnote for Tables 14.2.1.2 to 14.2.1.4 per SAP Section 6.11.2.2.>>

Table 14.2.1.5
 Multivariate Analysis of Progression-Free Survival (PFS) Based on Investigator's Assessment
 Intent-to-Treat Set

Prognostic Factors	----- Progression-Free Survival (Months) -----	
	Hazard Ratio (95% CI)	P-value
Treatment		
KW-0761 vs. Vorinostat	xx.x (xx.x, xx.x)	x.xxxx
Disease Type		
MF vs. SS	xx.x (xx.x, xx.x)	x.xxxx
Disease Stage		
IB/II vs. III/IV	xx.x (xx.x, xx.x)	x.xxxx
Blood Involvement		
Yes vs. No	xx.x (xx.x, xx.x)	x.xxxx
Region		
US vs. Japan	xx.x (xx.x, xx.x)	x.xxxx
US vs. Rest of World	xx.x (xx.x, xx.x)	x.xxxx
Japan vs Rest of World	xx.x (xx.x, xx.x)	x.xxxx
Age Group		
>=65 vs. <65 yrs	xx.x (xx.x, xx.x)	x.xxxx
Gender		
Male vs. female	xx.x (xx.x, xx.x)	x.xxxx
Race Category		
White vs. Black or African American	xx.x (xx.x, xx.x)	x.xxxx
White vs. Other	xx.x (xx.x, xx.x)	x.xxxx

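### The primary hazard ratio is covariate-adjusted while the primary p-value is stratified, so the headline estimate and the test can disagree near the significance boundary

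*SAP*

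**What the plan says.** SAP 6.11.2.1 makes the primary comparison of investigator-assessed PFS in the ITT set a "stratified Log-rank test at the one-sided 2.5% significance level", with disease type, disease stage and three-level region as the strata. For the size of the effect, the same section says "A Cox proportional hazard model with treatment, disease type, disease stage, and region (U.S., Japan, and Rest of World) as covariates will be used", and the reported hazard ratio and 95% CI come from that model.

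The shell for Table 14.2.1.1 puts both results in one treatment-comparison block. Its footnote attributes the hazard ratio and CI to the covariate model, then says "P-value (two-sided) is obtained from a stratified log rank test" with the same three factors as strata. The footnotes of the other PFS tables (14.2.1.6.2, 14.2.1.7.1, 14.2.1.8), the OS table (14.2.9.1) and the TTF table (14.2.10) make the same split.

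SAP 8.2.5 gives sample code:

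- Log-rank test (LIFETEST): "strata type stage region/group=trt". Region is handled as categories.
- Hazard ratio (PHREG): "model PFS*censor(1)=trt type stage region/risklimits ties=efron". There is no STRATA and no CLASS statement.
- Quality of life (MIXED): "class trt type stage region timept usubjid". Region is declared categorical.

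**The concern.** The stratified log-rank test compares the arms within each type-by-stage-by-region cell and lets every cell have its own baseline hazard. The covariate Cox model fits one baseline hazard and assumes that type, stage and region act proportionally on it. These are two analyses of the same data, and nothing forces them to agree. If the result is close to the boundary, the clinical study report could show a significant p-value beside a CI that includes 1, or the reverse, in the headline table of the trial.

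The sample PHREG code adds a smaller problem. Without CLASS, a region variable stored as a number gets a single slope across three unordered regions, and one stored as text stops the procedure with an error. Type and stage have two levels each, so a numeric code does no harm for them.

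**Working it through.** **Inputs from the documents.** One-sided alpha 0.025; 1:1 allocation; medians 169 and 254 days; 255 events; 24 months of accrual plus 12 months of follow-up; 288 subjects inflated by 10% to 317 (SAP 3.2.1, 6.3 and 6.11.2.1). The strata are type (2) × stage (2) × region (3), up to 12 cells.

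**The plan's own figure.** HR = 169/254 = 0.665 and ln HR = −0.4074. The Schoenfeld formula gives 4 × (1.960 + 1.282)² / 0.4074² ≈ 253.2, rounded up to 254 events, against 255 stated. Power with 255 events is Φ(0.4074 × √255/2 − 1.960) = Φ(1.293) = 0.902. Exponential PFS with uniform accrual gives an event probability of 0.885, so 255/0.8846 ≈ 288 subjects, and 288 × 1.10 ≈ 317. The design reproduces.

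**Where the boundary lies.** With 255 events the critical HR is exp(−1.960 × 2/√255) = exp(−0.2455) = 0.782. A true HR of 0.78 therefore sits almost on the boundary and is close to the worst case for disagreement.

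**Simulation.** There were 3,000 trials per scenario with N = 317, cut at 255 events. The documents give no region mix or effects, so the following are assumptions:

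- US/Japan/Rest of World mix of 50/5/45% or 40/20/40%
- log hazard ratio against the US of 0, 0.7 or 1.0 for Japan, and 0, 0 or −0.3 respectively for Rest of World
- 45% Sézary syndrome, all stage III/IV
- numeric codes US = 1, Japan = 2, Rest of World = 3

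The table gives the share of trials in which the stratified log-rank verdict and the 95% CI disagreed, as a range over the six region scenarios.

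| True HR | Cox as coded (region one slope) | Cox, covariates, region in CLASS | Cox stratified by type, stage, region |
|---|---|---|---|
| 0.665 | 3.8–8.1% | 3.7–4.3% | 0.0–0.1% |
| 0.78 | 7.9–15.6% | 7.7–9.1% | 0.0–0.4% |
| 1.00 | 1.2–2.1% | 1.1–1.4% | 0.0–0.1% |

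**Size of the gap in the estimate.** The 95th percentile of the ratio between the coded HR and the stratified HR was 1.06–1.15. With region in CLASS it was 1.062–1.075.

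**How much is due to coding.** With no region effect and true HR 0.665, one-slope and CLASS versions differed by about 2% in HR (95th percentile) and in verdict in 0.6–0.7% of trials. With Japan at 20% and the strongest non-monotone effects, the mean HR was 0.688 as coded against 0.662 with CLASS, and verdicts differed in 8.3% of trials. In most scenarios the larger share of the disagreement comes from stratifying versus adjusting, which CLASS alone does not remove.

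**Type I error of the test.** At HR 1 the log-rank test rejected in 2.6–2.8% of trials. The Monte Carlo standard error is √(0.025 × 0.975/3000) ≈ 0.3 percentage points, so this is consistent with 2.5%.

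**Not covered.** Times were continuous, so ties from 4-weekly visits were not simulated. Region effects entered as constant hazard ratios, so departures from proportionality across regions were not examined.

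**The case against.** A covariate-adjusted Cox model is a legitimate, pre-specified estimator. The SAP gives the two analyses separate roles, discloses the split in the table footnotes, and ties no decision rule to the Cox interval. That stands: this is a question of coherent reporting, and the confirmatory inference is sound.

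Stratifying the Cox model also has a cost. Up to 12 cells are formed, and events in a cell with only one arm at risk add nothing to the estimate, whereas the adjusted model uses them. At HR 0.665 the stratified Cox CI excluded 1 in 86.9–87.9% of simulated trials, against 89.4–89.8% for the adjusted model with CLASS. The primary log-rank test already accepts that loss (87.0–87.9%), so the change gives up nothing the test had kept.

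A reader might infer from the PHREG line that the plan analyses region as a linear score. The documents do not support that. SAP 8.2.5 presents the code as illustration, SAP 6.11.2.1 names three regions with no ordering, and Table 14.2.1.5 shows pairwise region contrasts that a single slope could not represent freely. The storage type of the variable is not given, and a text variable would fail visibly. The missing CLASS statement is a code slip to correct.

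**Conclusion.** The mismatch is real and sits in the SAP text and table footnotes as well as in the sample code. It can leave the headline HR and CI at odds with the primary p-value: in about 4–8% of trials at the design HR of 0.665, 8–16% at HR 0.78 and 1–2% at HR 1, for the model as coded. These ranges rest on assumed region mixes, region effects and a numeric region code; the upper ends need a sizeable Japanese share and strong, non-monotone region effects.

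A reader might go further and infer that the primary test is invalid or its error rate inflated. It is not: the p-value does not use the Cox model, and the simulated size was close to nominal. The point is a cheap improvement to reporting. It leaves the event count and sample size unchanged.

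**What to change.** In SAP 6.11.2.1, take the primary HR and 95% CI from a Cox model stratified by exactly the factors of the primary log-rank test, with treatment as the only covariate. In the PHREG code this means moving type, stage and region from the MODEL statement to a STRATA statement. Without ties, the score test of that model is the stratified log-rank test, which is why so little disagreement remains. Keep the covariate-adjusted model as a supportive analysis, and declare region in CLASS wherever it is a PHREG covariate.

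Change the footnote of Table 14.2.1.1 to match, and align the other PFS tables and the exploratory OS and TTF tables. The cost is one SAP sentence, two lines of code and the matching footnotes.
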